2.10 DATA COLLECTION

This trial will be coordinated from the CTU at LSHTM and conducted at GP practices in England and Wales.

Baseline data will be collected at each GP practice by the GP or Research Nurses, and will be entered directly online to the trial database provided by the LSHTM CTU. Follow up data will be collected directly from each patient at the end of each two-month period.

Patients will be allowed to choose the method of data collection most suitable for them from the following:

1. Bespoke mobile app which will require patients to use their own smartphone.
2. Online database using a computer, phone or tablet.
3. Paper forms which they will receive by post at the same time with their trial treatment and which they can complete themselves or they can request a trial team member to contact them by phone to help with completing the forms.
4. Trial staff will telephone the patient on each data collection day and complete the questionnaire based on the patient answers.

For patients with a smartphone who choose to submit outcome data using the trial's bespoke mobile app, the Research Nurse will help the patient to install and set-up the app for use. The Research Nurse will also give a demonstration to ensure the patient understands how to use it. Each nurse will have access to the internet so that the patient can download the app without using their own mobile network (ensuring that download of the app is free of charge to the patient).

The GP or Research Nurse will also help the patient to complete the symptoms data for the Baseline form (Appendix 2) using their preferred method. Any questions can be addressed at this stage. Once baseline procedures have been completed and the patient confirmed as being eligible and consented, the patient can then be randomised.

A screening log will be used to record all patients who were identified as potentially eligible using the GP practice database, including those who were ineligible and those who declined participation. The Screening Log will remain at the relevant GP practice and only anonymised information regarding number of screened patients and number and reasons for screen failure will be shared with the CTU.

Only data outlined on the baseline, follow up, end of trial and adverse events data forms will be collected as part of the trial database.

2.10.1 BASELINE AND RANDOMISATION DATA

Baseline data will be collected by the GP or Research Nurse performing the assessment at the Screening Visit (Appendix 2). Baseline data will be collected via a bespoke online trial database, to which each GP and Research Nurse will have a unique log-in ID and password. Eligible patients will then be randomised and data about the randomisation (date, time and randomisation number) is generated.

2.10.2 TREATMENT PHASE FOLLOW UP DATA

In the seventh week of each treatment period, patients will receive reminders (format agreed at baseline) to alert them that follow-up data collection is approaching. During the 8th week of each treatment period, the Patient Questionnaire and VAS Pain Scale forms (Appendices 4 and 5) will be completed by the patient. Patients can choose to receive daily reminders on each day their data is due to be collected. Non-responders will automatically receive a reminder after 24 hours of due date by the trial team.

2.10.3 END OF TRIAL DATA

During the seventh week of treatment period 6, the Research Nurse will contact patients to thank them for their participation so far, inform them that this is the last treatment period, and that they, together with their GP, will receive their individual results at the beginning of month 14. The Research Nurse and patient will arrange a telephone or face-to-face appointment to discuss the individual results during month 14. The Research Nurse will also inform patients that if they want to continue taking a statin without a break, to arrange a separate clinical appointment with their GP prior to the end of the treatment period.

At month 15, trial staff will email/telephone the patient to document their decision on future statin use and whether their results helped reach this decision. This will be the last data collection point of the trial.

Throughout the trial, continued patient care will be at the discretion of their GP. In primary care, the patient will be recorded as having an ongoing statin prescription.

- Where treatment with an interacting drug is needed that will be for less than one-month duration, the patient will be asked to stop the trial treatment for that period.
- Where treatment with an interacting drug is needed for longer than one month, the patient will be asked to withdraw from study treatment completely.

When the patient is randomised, a temporary Read code indicating StatinWISE participation will be recorded in their primary care record, the code will be removed at the end of the trial.

Patients will also be given an alert card that identifies them as a StatinWISE patient. Patients will be asked to present this card to anyone providing medical care outside of their usual general practice. This card will have a link to the trial website and a trial contact number.

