2.4 SAMPLE SIZE

A sample size of 64 participants provides approximately 90% power to detect a treatment effect of at least 10mm, assuming a Type I error of 5%. Allowing for loss to follow-up of 40% of participants through the trial inflates the required sample size to 107 participants.

Period effects (changes in underlying VAS pain score due to factors other than randomised treatment, e.g. seasonal, activity-related, etc.), variability in individual statin effects across patients, and imperfect adherence to the assigned treatment were investigated by further detailed simulations. VAS pain scores are not normally distributed, since they are bounded (0-100mm) and can display large fluctuations in response. Therefore, further power calculations were performed drawing the outcome from a Beta distribution, and from a distribution with normal variance components on a logit scale, to assess the robustness of the sample size estimates to the distribution chosen. These factors all have the effect of decreasing power, thus increasing the sample size required. An approximate 80% increase in the sample size required in the absence of these effects provided approximately 90% or more power across a plausible range of these potential effects, thus we determined that a final sample size of 200 was required.

Multiple testing: Rather than making formal adjustments for multiple testing, we follow an approach advocated by Pocock²⁵ of clearly specifying our primary analysis (which provides a single test for treatment effect), while explicitly presenting and interpreting all other tests as secondary analyses.

Power for individual N-of-1 trials: In order to increase the statistical power for the analysis of individual N-of-1 trials, we will ask participants to report symptoms daily in the last week of each period, rather than once per period. Full adherence through the trial will provide between 55 and 70% power to detect effects of 10mm or greater for individual treatment comparisons.

Estimates of recruitment and retention rates: We anticipate that some patients will not complete data in each treatment period, and that some will not complete their 12-month follow-up. By designing this study as a series of N-of-1 trials, which offer individual participant benefit in the form of an individualised estimate of effect, we hope to minimise this type of dropout. However, we have accounted for this in our sample size calculation by allowing for 40% loss to follow-up.

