2.6 RECRUITMENT OF PARTICIPANTS

Participants will be recruited directly from GP Practices or by advertising to the public.

Participating practices will recruit eligible patients from two groups as follows:

1) Patients who are considering discontinuation of their statin due to muscle symptoms:

These patients will be invited to take part in the trial when they visit the GP to report muscle symptoms believed to be associated with statins and where the patient/GP is considering stopping statins because of the muscle symptoms. The GP or Research Nurse will approach the patient and give the patient information sheet (Appendix 6 and Appendix 6a). If interested, patients will be able to consent (Appendix 7 and Appendix 7a) and complete the screening visit with the GP or the Research Nurse during this appointment or it can be arranged for another suitable time.

2) Patients who have stopped taking a statin in the last 3 years due to muscle symptoms:

A search of the practice electronic records will be performed by the Research Nurse on a two-monthly basis for one year (or until recruitment targets are reached) to identify potentially eligible patients. All screened patients will be documented on a screening log. The list will be reviewed by the GP to confirm clinical eligibility before patients are invited to take part. A letter inviting them to attend a screening visit, accompanied with the patient information sheet (Appendix 6 and Appendix 6a) for the patient to consider, will be sent by the trial team from their GP practice. Contact details of the Research Nurse will be provided should the patient have any questions. A reply slip will be enclosed for the patient to complete if they wish to attend the screening visit, which will be returned to the Clinical Trials Unit (CTU), during which the trial will be explained, and they will have the opportunity to ask questions. Patients will be sent a letter of invitation to consider participation up to a maximum of three times.

3) Patients who contact the CTU from advertising:

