2.9.1 DOSE SELECTION

Atorvastatin is recommended by the current NICE guidelines for lipid modification;² 20mg is the recommended dose for primary prevention of cardiovascular disease. Atorvastatin is also recommended by NICE for secondary prevention² and for patients with a high risk of adverse events (our patient population), a dose lower than 80mg is recommended. The most commonly used dose is 20mg. A visually matched placebo has been chosen as an appropriate comparator for two reasons. Firstly, patient expectation of symptoms while on statins is likely to affect their experience of symptoms. A placebo control should minimise bias arising from knowledge of allocation. Secondly, withholding statin treatment from patients during placebo treatment periods is justified because the trial will recruit patients who have recently stopped using statins (and therefore are not currently receiving any benefit from statins) and those who wish to discontinue. If patients in the trial tolerate the active treatment periods with few symptoms, then this trial is likely to increase their usage of statins in the long term.

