2.17 ANALYSIS

Individual N-of-1 trials: The purpose of these analyses is to inform the individual patient of the effect of the IMP on their VAS muscle symptom score. The analysis and presentation of individual level results will be developed in collaboration with the Patient and Public Involvement (PPI) group. We will examine a range of graphical summaries and statistical analyses in order to identify the most informative presentation of individual results. As a result of this process, at the end of each individual trial the participant will be shown numerical and graphical summaries of their individual data, in relation to their IMP and placebo periods.

Combined analysis of N-of-1 trials

Primary analysis: To estimate the population average estimate of the trial treatment n VAS muscle symptom score, data from each N-of-1 trial will be aggregated to form a powerful dataset. We will adopt an intention-to-treat approach. Patients who enter data on muscle symptoms at least once during a treatment period with the IMP and at least once during a treatment period with placebo will be included in the primary analysis.

The primary analysis will be a linear mixed model for VAS muscle symptom score with random effects for participant and treatment and fixed period effects. Residual errors will be modelled using

a first-order auto-regressive error structure within each treatment period to account for correlation between the 7 daily measurements, with robust standard errors to account for non-normality of the VAS scores. Although VAS muscle symptom scores are unlikely to be exactly normally distributed, analysing such data using normal-based methods is likely to be a sufficiently robust approach.²⁶ All tests will be two-sided. $p < 0.05$ will be considered statistically significant.

Secondary analyses: Secondary outcomes relating to the impact of the IMP on other aspects of life will be analysed in a similar manner to the primary outcome, omitting the auto-regressive correlation structure since these secondary outcomes are measured once per treatment period. We will investigate whether the excess muscle symptoms, if any, experienced during treatment periods with the IMP appears to be concentrated in multiple sites.

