Appendix 4: StatinWISE Patient questionnaire

INSTRUCTIONS

This questionnaire is to be filled out once every two months (on day 56). We will remind you one day before it is due. Please answer all questions. If you need any help to complete the form. Please call our Freephone number [name] or email the study team: [contact].

PART 1: ADHERENCE TO MEDICATION

Step 1 (all participants):

Q1. How would you best describe your use of study medication in the past two months? (Please choose one of the following options)

- I didn't take my study medication at all
- I took my study medication on some days
- I took my study medication on most days, but missed an occasional dose
- I took my study medications every day

Step 2 (appears if the participant chooses "I didn't take my study medication at all", or "I took my study medication on some days"):

Q2. What was the reason that you didn't take your study medication every day in the past two months? (please tick all that apply)

- I forgot to take my study medication

Ticking the above will prompt the following option, if ticked, the trial team will action:

- Would you like a daily reminder sent to you via email/push notification

- I was prescribed another medication and my doctor told me to stop taking my study medication

Ticking the above will prompt an alert for the trial team to contact surgery for details and consider withdrawal from study

- My doctor recommended that I stop taking study medication because of muscle symptoms

Ticking the above will prompt an alert for the trial team to contact surgery for details

- I decided to stop taking study medication because of muscle symptoms

Ticking the above will prompt an alert for the patient to contact the GP for advice

- I didn't want to take my study medication

Ticking the above will prompt the following option, if ticked NO, the trial team will arrange for end of trial:

Do you still wish to participate in the trial: Yes No

- Other (please specify)

(free text)

PART 2: EXPLORING SYMPTOMS IN THE PAST TWO MONTHS

1. *(all participants):* In the last two months, have you experienced muscle symptoms, e.g. muscle pain or weakness?

Yes
 No

2. *(appears if the participant ticks yes for Question 1):* Do you think these muscle symptoms are related to your study medication?

Yes
 No
 Don't know

[figure not shown]
3. *(appears if the participant ticks no for Question 2):* What do you think may have caused these muscle symptoms?
(free text)

Don't know

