2.3.7 SECONDARY ANALYSES

Withdrawal, Loss to follow-up and Adherence – Descriptive analyses

Loss to follow up and withdrawal, with reasons for withdrawal, will be summarized by overall frequencies and percentages. Protocol violations will be tabulated. Descriptive statistics, including graphical summaries, will be used to summarise the measures of adherence to randomized treatment and withdrawal, and their relationship to the statin and placebo periods.

Withdrawal – Comparison between statin and placebo periods

We will explore whether the period in which a patient was first known to have withdrawn was more likely to have been a placebo or a statin period. If this date is after the end of a treatment period but the patient chooses not to begin the next period, the period in which the withdrawal happens will be set to the period just ended.

Adherence – Randomised comparison

We will explore whether adherence was lower on statin periods compared with placebo periods using mixed models similar to those described above.

Adherence – Efficacy analyses

We will use the measures of adherence to randomised treatment to perform an efficacy analysis based around an instrumental variables approach. Because these analyses require much stronger assumptions than the intention-to-treat analysis above, the results of the efficacy analysis will be presented and interpreted as a secondary analysis.

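### No form used in the six treatment periods records statin taken outside the trial, so any such use would be unseen and the adherence-based efficacy analysis could not correct for it

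*Protocol*

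**What the plan says.** Protocol 2.6 names as its first recruitment group "Patients who are considering discontinuation of their statin due to muscle symptoms", and Protocol 2.7 makes such patients eligible alongside those who have already stopped. Protocol 2.9.1 argues that "withholding statin treatment from patients during placebo treatment periods is justified", so the intended contrast is statin against no statin. Protocol 2.10.3 adds, for the duration of the trial, that "In primary care, the patient will be recorded as having an ongoing statin prescription".

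Exposure during treatment is measured in three ways:

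- Part 1 of the day-56 questionnaire (Protocol Appendix 4) asks "How would you best describe your use of study medication in the past two months".
- The daily form (Protocol Appendix 5) asks whether study medication was taken the day before.
- SAP 1.8 adds a count of capsules left in returned packs.

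Protocol 2.10 states that "Only data outlined on the baseline, follow up, end of trial and adverse events data forms will be collected" for the trial database. SAP 2.3.7 then says "We will use the measures of adherence to randomised treatment to perform an efficacy analysis based around an instrumental variables approach"; Protocol 2.17 plans the same. SAP 2.3.2 also plans to split the symptom descriptions by the treatment that patients actually received.

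**The concern.** The question put to each patient, and to the whole dataset, is whether symptoms are worse on statin than off it. That reading needs the placebo periods to be free of statin, or at least needs departures to be known. Some participants enter while taking their own statin, yet no measure in the treatment phase could reveal whether any of them took it during the trial.

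Three outputs depend on this. The intention-to-treat difference would understate a real effect of statin versus none, which matters most if the result is close to zero. The efficacy analysis is meant to correct for departures from allocation, but it would correct only for missed capsules. The individual results given to patients are also affected: someone taking their own statin throughout would have compared added trial statin with no addition, and nobody could tell. Analysts cannot recover the information after data collection ends.

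**Working it through.** **1. What each form can show about statin use**

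| Time | Source | What is asked |
|---|---|---|
| Before treatment | Baseline form, items 11 and 26 | Statin use in the last 3 years; all current medication |
| Each treatment period | Questionnaire, Part 1 | Use of study medication; reasons for missing it |
| Each treatment period | Daily form | Study medication taken yesterday |
| Each treatment period | Pill count (SAP 1.8) | Capsules remaining, 0 to 56 |
| After period 6 | End of trial form, item A.3 | Statin prescription in the following 4 weeks |

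One Part 1 option mentions another prescribed medication. It appears only to patients who took study medication on no days or some days, and it concerns a doctor's advice to stop study medication. It does not ask about statins. The gap is therefore the 12 treatment months.

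**2. The plan's own sample size**

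Inputs: effect 10 mm and power about 90% (Protocol 2.4); "assuming a Type I error of 5"%; "All tests will be two-sided" (Protocol 2.17); three statin and three placebo periods per person (Protocol 2.8). The difference of two three-period means has variance σ²(1/3 + 1/3) per person.

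- With σ = 30: variance = 900 × 2/3 = 600, and N = 600 × ((1.960 + 1.282)/10)² = 63.04, so 64. Power at 64 is 90.4%.
- With σ = 25: N = 44, and power at 64 is 97.5%.

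Protocol 2.3 gives both values for the within-participant SD. Only 30 reproduces the stated 64, so it is used below. Loss of 40% gives 64/0.6 = 107, as stated. Of the planned 200, 200 × 0.6 = 120 remain evaluable.

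**3. Dilution**

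Assumptions, none of them from the documents:

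- A fraction c of participants take their own statin irrespective of the blinded period.
- It acts like the trial statin.
- Taking both adds no further effect.

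Let a be capsule adherence in statin periods.

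- Exposure in statin periods: c + (1 − c)a. In placebo periods: c. The contrast is a(1 − c).
- Intention-to-treat difference for a true 10 mm effect: 10·a(1 − c).
- Efficacy estimate scaled by capsule adherence alone: 10·a(1 − c)/a = 10(1 − c), whatever the value of a.
- Efficacy estimate scaled by any statin taken: 10·a(1 − c)/[a(1 − c)] = 10.

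For example, with a = 0.9 and c = 20%, the intention-to-treat difference is 7.2 mm. Dividing by 0.9 gives 8.0 mm; dividing by 0.72 gives 10 mm.

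**4. Power with 120 evaluable participants, σ = 30, a = 1**

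SE = √[(600 + 100·c(1 − c))/120]. The added term is the variation in individual effect between users and non-users of own statin.

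| c | Apparent effect (mm) | Power |
|---|---|---|
| 0 | 10.0 | 99.4% |
| 5% | 9.5 | 98.8% |
| 10% | 9.0 | 97.9% |
| 20% | 8.0 | 94.2% |
| 30% | 7.0 | 86.8% |

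At c = 20%: SE = √(616/120) = 2.266, 8/2.266 = 3.531, and Φ(3.531 − 1.960) = 94.2%.

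**The case against.** The strongest reply is that nothing in the documents shows such use happening. The record sentence in Protocol 2.10.3 comes directly before the rules on interacting drugs and shortly before the trial Read code and alert card. It may serve only to make a blinded patient appear statin-exposed to other prescribers. The same section tells patients who want a statin without interruption after period 6 to book a GP appointment, which suggests that no supply is running. Every participant has stopped, or is thinking of stopping, because of muscle symptoms, so a second statin is not an obvious choice. This stands. A reader might infer from 2.10.3 that patients keep receiving their own statin, or that the comparison is already biased; the documents support neither inference.

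Nor can the absence of an instruction to stop be held against the plan. The patient information sheet, the written dosing instructions and the adverse event form were not available, and such an instruction may be there. But an instruction is not a measurement. SAP 2.3.7 tabulates protocol violations, yet none of the treatment-phase measures shown would detect this one.

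Three further readings go too far:

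- That no trial form asks about statins at all: the baseline and end-of-trial forms do.
- That patients who stop study drug under Protocol 2.10.4 form a second route to own-statin use: none of the options listed there adds a statin.
- That the efficacy estimate falls further than (1 − c), for example to (0.85 − 0.20)/0.85 = 76% of its true value with an assumed 85% adherence and c = 20%. That requires use in placebo periods only, which blinded patients could not target.

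Finally, the sample size already includes a margin for imperfect adherence among other factors, and the efficacy analysis is secondary and flagged as needing stronger assumptions. Both points are fair. They limit the consequence but do not close the measurement gap.

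**Conclusion.** The measurement gap is real: during the six treatment periods no form shown records non-trial statin use, although current users are eligible and the rationale for placebo relies on statin being withheld. Whether this leads to any dilution depends on a rate the documents do not give. Under the assumptions in the working, both the intention-to-treat and the efficacy estimates shrink by the factor (1 − c), that is by 5%, 10% or 20% at those values of c. If the statin has no effect on symptoms, or c is zero, nothing changes.

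The comparison by allocation remains valid as a comparison of allocated treatments, and power is not the problem at plausible values. What is weakened is the reading of the result as statin versus no statin, above all for a null finding, and the ability of the efficacy analysis to do what it is for. This is a cheap improvement worth making, not a flaw that invalidates the design.

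**What to change.** Add one item to Part 1 of the day-56 questionnaire, in every data-collection mode: has the patient taken any statin other than study medication in the past two months (no / some days / most or every day), with name and dose.

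In SAP 1.8 and 2.3.7, define exposure for the efficacy analysis as any statin taken, and tabulate non-trial statin use by allocated treatment. If the table is nearly empty, it strengthens the interpretation of a null result.

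Reconcile the ongoing-prescription sentence in Protocol 2.10.3 with the withholding rationale in 2.9.1, so that the meaning of the record entry is clear. What the clinical arrangement should be is for the trial team to decide.

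The cost is a slightly longer form, a short SAP addition and one clarified sentence.
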